## **2. Objectives**

### **Specific Aims and Research Hypotheses**

The proposed study is designed to achieve the following specific aims:

**Aim 1.** To explore whether dexamethasone (DEX), a cortisol analogue, administered 10+ hours prior to the virtual reality exposure (VRE) therapy session, enhances exposure therapy in humans with PTSD as compared to pill placebo;

**Aim 2.** To explore whether any enhancement in exposure therapy produced by DEX in VRE evidenced within session and immediately post-treatment results in long-term gains in treatment response as compared to pill placebo.

*The following hypotheses will be tested:*

- 1) DEX will facilitate fear extinction in humans. It is predicted that the patients who receive VRE combined with 0.5 mg DEX + 10hr will evidence more improvement on symptom measures, and on reduced psychophysiological arousal measured via startle, skin conductance, and heart-rate responses during exposure to Iraq or Afghanistan military scenes, than the placebo group. Furthermore, DEX + VRE will result in faster improvement in symptoms (fewer sessions to reach 70% reduction in symptoms), and fewer drop-outs (i.e., better tolerance of exposure therapy).
- 2) Facilitation of therapeutic response aided by DEX will result in long-term gains. It is predicted that the group of patients who receive VRE combined with 0.5 mg of DEX will evidence more improvement on a follow-up assessment gathered 3, 6, and 12 months post-treatment as compared to baseline on symptom measures and reduced startle, skin conductance, and heart-rate responses during exposure to Iraq or Afghanistan military scenes than the group who receives placebo.

Exploratory analyses of genetic markers will examine predictors of treatment response. The long-term goals include furthering translational research and directly applying paradigms shown successful in animals to humans. For this specific paradigm, we plan to establish whether DEX can facilitate exposure therapy and apply this knowledge to other disorders. Random assignment of participants to placebo or active conditions, standardized treatment delivery, homogeneous DSM inclusion criteria, and blind independent assessment will assure a methodologically rigorous study.

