#### Measures at each Therapy Session

Expectancy of Therapeutic Outcome Questionnaire (ETOQ) assesses how logical the treatment appears, and the expectancy of success for the patient and for others. This measure is administered after session 1 only.

Clinical Global Impressions Scale, Severity of Illness (CGI-Severity; Guy & Bonato, 1970). This is a study personnel rated measure of severity of illness ranging from 0 (not assessed) to 7 (among the most extremely ill patients). This measure is administered after sessions 1–6.

Clinical Global Impression – Improvement (CGI-Improvement; Guy & Bonato, 1970). This is a study personnel rated measure of patient's improvement since start of study ranging from 1 (very much improved) to 7 (very much worse). This measure is administered after sessions 2-6.

Clinical Global Improvement Scale, Patient Report (CGI - Self Report; Guy & Bonato, 1970). This is a self-reported global measure of change in severity of symptoms, ranging from 1 (*very much improved*) to 4 (*unchanged*) to 7 (*very much worse*). This measure is administered after sessions 1-6.

The PTSD Symptom Scale is a 17-item interview used to aid in the detection and diagnosis of PTSD (described above), administered before sessions 2-6.

Subjective Units of Discomfort (SUDs) will be gathered during each exposure session (sessions 2-6). Participants will be asked to rate their level of discomfort on a scale of 0 (no anxiety) to 100 (panic levels of anxiety) every 5 minutes during the VR exposure.

Intent to Attend (Leon et al., 2007) is a short, two question survey asking participants how likely they are to complete all of the study and how likely they are to attend the next session.

Blinded Medication Check is a one-question measure to assess which medication the participant believes they took.

Cortisol Sampling will be obtained from saliva in order to measure post-dexamethasone cortisol levels and detect the presence of dexamethasone in saliva. Cortisol sampling methods are described below.

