### 10.2 Statistical Analyses

#### Power and Sample Size

Power calculations are based on Cohen (1992). We set the Type I Error rate at 0.05 (two-tailed) for all computations. We first calculated the number of participants needed to test the effect of VRE augmentation with DEX at immediate post-treatment assessment (Hypothesis 1 above). Then, knowing how many participants would be needed at the end of this phase, we worked backward to calculate how many participants would need to be enrolled initially. We will continue to collect data from all participants, including those who drop out of treatment or are discontinued. Thus, loss to the study represents a failure to participate in measurement, and not merely dropout from treatment. We assumed that: (1) 10% of participants will be lost to the

study by the end of treatment; an additional 15% of participants will drop out of treatment, resulting in 25% of participants randomized to placebo or 0.5mg DEX groups that would not complete treatment. We anticipate that 10% of completers will be lost to the study prior to the 3 month follow-up visits.

The effect size measure used,  $d$ , represents the standardized difference between sample means. Cohen (1988) has proposed that  $d = .30$ ,  $.50$ , and  $.80$  be categorized as “small,” “medium,” and “large,” respectively. We assume that a medium effect size—half a standard deviation—is the smallest clinically meaningful difference between DEX-augmented VRE vs. placebo-augmented VRE at the end of treatment.

For a two-group study design, 100 participants ( $n=50$  in each group) would be needed to achieve a minimum desired power of 85% to detect an effect size of  $.65$  with a 2-sided test at a significance level of 0.05.

Hypothesis 1: Patients who receive VRE+DEX will evidence more improvement on within-session measures (SUDs), on immediate post-treatment symptoms measures and on startle, SCR and HR, than the group who receives placebo.

To analyze pre-treatment and immediate post-treatment differences, the first analysis will compare the VRE+DEX condition to the VRE+placebo condition on the following outcome measures: 1) symptom measures (continuous variables); 2) psychophysiological measures (startle responses, cortisol levels, heart-rate, skin conductance) (continuous variables). It is expected that VRE+DEX participants will show significant improvement on all outcome measures immediately post-treatment compared to VRE+ placebo participants.

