Continuous variables will be analyzed using multivariate repeated measures ANCOVA with treatment condition being the between subjects factor, the pre-treatment vs. post-treatment condition being the within subjects factor, and the scale scores as the multiple measures accounting for appropriate covariates as determined through preliminary analyses discussed above. Adjusted means and mean differences as well as interaction terms will be obtained and evaluated. Categorical variables will be analyzed using logistic regression and controlling for appropriate covariates resulting in adjusted odd ratios.

An additional approach to testing this hypothesis will involve using two categorical measures of clinically significant improvement: 1) a 30% decrease in the CAPs, and 2) a rating of “much improved” or “very much improved” by the therapist and participant on the CGI inventory at the end of active treatment. These data will be analyzed using logistic regression with the inclusion of appropriate terms for the covariates and treatment-by-covariate interactions.

Furthermore, we will look at the number of sessions required to reach 70% improvement or maximum treatment response and the number of dropouts, predicting fewer sessions to reach 70% improvement or maximum treatment response and fewer dropouts in the VRE + DEX group.

Within-subject measures will also be obtained to assess improvement within sessions. SUDS and psychophysiological measures (heart rate and skin conductance) will be used to measure within session anxiety levels. Average and peak values of these continuous variables will also be analyzed using a repeated measures ANCOVA.

Hypothesis 2: Patients who receive VRE+DEX will evidence more improvement on follow-up assessments (symptom measures and psychophysiological responses) gathered 3, 6 and 12 months post-treatment compared to the patients who receive the placebo.

*Interval specific analyses:* First, the effectiveness of the VRE+DEX treatment will be analyzed for the two interval periods separately: from immediately post-treatment to the 3, 6 and 12 -month assessment. To test these time interval specific treatment effects, logistic regression will be used to compute adjusted odd ratios for dichotomous outcomes and multivariate

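### The within-session analysis names only average and peak, which cannot separate a fall in anxiety from a lower start, and it uses heart rate and skin conductance that are not scheduled at therapy sessions

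*Combined protocol and SAP*

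**What the plan says.** Under Hypothesis 1, section 10.2 gives the purpose: "Within-subject measures will also be obtained to assess improvement within sessions". It then names the variables: "SUDS and psychophysiological measures (heart rate and skin conductance) will be used to measure within session anxiety levels". The analysis is one sentence: "Average and peak values of these continuous variables will also be analyzed using a repeated measures ANCOVA". No slope, start-to-end or peak-to-end change is defined anywhere. The text does not say whether the repeated factor is time within a session or session number.

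Section 10.2 words the hypothesis as "Patients who receive VRE+DEX will evidence more improvement on within-session measures (SUDs", and lists skin conductance and heart rate separately with the other outcomes. The hypothesis in section 2 opens with "DEX will facilitate fear extinction in humans". Aim 2 builds on enhancement seen within session.

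On data collection, section 8.0 (Measures at each Therapy Session) states: "Subjective Units of Discomfort (SUDs) will be gathered during each exposure session (sessions 2-6", with a rating every 5 minutes. That list also includes saliva sampling but no heart rate or skin conductance.

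**The concern.** Improvement within a session is a change, whereas average and peak describe how high anxiety was. The difference matters here because the protocol expects two separate effects. One is better extinction during exposure (section 2). The other, in the section on significance of the research, is less fear before the session begins. The second effect alone would lower both average and peak, with no extra fall during exposure.

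The planned analysis could therefore report within-session improvement that is only a lower start, or miss a steeper fall that did occur. The ratings needed to tell these apart are already collected.

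The heart rate and skin conductance part has a different problem: the analysis names data for which the schedule provides no source.

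**Working it through.** The plan states no figure on this point, so there is none to reproduce.

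**Step 1: ratings per session.** SUDs are rated every 5 minutes (Measures at each Therapy Session) over at most 45 minutes of exposure (Interventions). That gives 45/5 + 1 = 10 ratings. Sessions 2-6 are five sessions, so up to 5 × 10 = 50 ratings per participant.

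**Step 2: what the summaries register.** Take an illustrative session of 80, 80, 75, 70, 60, 50, 45, 40, 35, 30.
- Average = 565/10 = 56.5; peak = 80; start minus end = 80 − 30 = 50; least-squares slope = −6.2 per 5 minutes.
- The same ratings in reverse: average 56.5; peak 80; start minus end = 30 − 80 = −50; slope = +6.2.

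Average and peak are identical for a 50-point fall and a 50-point rise. This needs no assumption about the trial.

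**Step 3: how much decline each summary picks up.** Suppose arms start equal and one falls b points more per rating. The rating index runs from 0 to 9 with mean 4.5. The average then shifts by 4.5b and start minus end by 9b, while the peak, usually near the start, hardly moves.

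A simulation shows the pattern. All its values are assumptions, not protocol figures: one session, 50 per arm, starting mean 75 (SD 15), mean fall 3 points per rating (SD 1.5), rating noise SD 6, scores limited to 0-100, t-tests at two-sided 0.05, and 4,000 simulated trials per row. Decline is start minus end. Entries are the share of trials with a significant difference.

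| Assumed effect of DEX | Average | Peak | Decline |
|---|---|---|---|
| Start 10 points lower, same rate of fall | 85% | 87% | 5% |
| Falls 1 point more per rating, same start | 27% | 6% | 79% |
| Falls 1 point more per rating, start 4.5 higher (average shift 4.5 − 4.5 × 1 = 0) | 4% | 20% | 76% |

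In the first row, average and peak detect a pure level effect and decline stays at about the nominal 5%. In the second, the average has some sensitivity and the peak almost none. In the third, the average is blind. The peak's 20% arises from the higher start, so it tends to count against DEX.

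**Step 4: where heart rate and skin conductance are scheduled.**
- Measures at each Therapy Session: SUDs and saliva; neither measure listed.
- Section 6.0 and Interventions: SUDs are the only rating described during exposure.
- Collection of Salivary Samples: on intervention days, saliva on arrival.
- Pre-Treatment Assessment: both measures, during a 15-minute viewing of VR scenes.
- Post treatment and follow-up assessments: both measures, in response to the VR scenes.
- Psychophysiological Data Collection and section 9.0: recording methods and data sources, with no therapy-session time point.

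So the phrase "psychophysiological measures (heart rate and skin conductance) will be used to measure within session anxiety levels" in section 10.2 has no matching entry in the schedule.

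**Step 5: timing of the initial rating.** Under Interventions, the pill is taken before each VRE session from session 2 onward. Every session's first SUDs rating in sessions 2-6 therefore follows dosing.

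**The case against.** The strongest reply is that level is a legitimate target. Section 10.2 itself speaks of anxiety levels within session, the preliminary-studies section argues that reducing fear expression may help treatment, and Hypothesis 1 in section 2 predicts lower arousal during exposure to military scenes. This stands. A reader might infer that average and peak are the wrong outcomes and should be replaced. The documents do not support that: the two summaries fit one stated interest and fail only to isolate the other.

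Nor is it right that the average carries no information about decline. With equal starts it carries some (27% against 79% above). If the repeated factor is session, average and peak would also show change between sessions, but that is not the within-session improvement named as the purpose.

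Decline measures have weaknesses too. Section 6.0 and Interventions have the therapist continue exposure until anxiety comes down, so the last rating and the number of ratings depend partly on response. Peak minus last is the more exposed to this. A lower start also leaves less room to fall, so any decline measure can understate a benefit of DEX. Adjusting for each session's initial SUDs might look like the remedy. But that rating follows the pill and the protocol expects the drug to change it, so adjusting would condition on a likely mediator and weaken the randomised comparison.

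On physiology, a reader might infer that session recordings will not be made and are lost. The documents show only that they are not scheduled, while section 10.2 states an intent to use them. Reading session as the 15-minute assessment would supply data, but SUDs, named in the same sentence, are listed only at therapy sessions.

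**Conclusion.** The point holds in a limited form. Average and peak measure level and cannot separate a fall during the session from a lower start, which is the distinction that improvement within sessions requires. That conclusion is arithmetic. The simulated percentages illustrate its possible size and rest on assumed values; with five sessions per participant the actual power would differ.

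The schedule gap also holds, for heart rate and skin conductance only. SUDs are scheduled, and Hypothesis 1 in section 10.2 labels only SUDs as within-session.

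The weight is moderate. The aims are exploratory, the sample size rests on the post-treatment comparison, and the 5-minute SUDs are collected in any case, so decline can still be derived. A reader might infer that the main efficacy result is compromised; nothing here touches the post-treatment symptom comparison.

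**What to change.** 1. Keep average and peak SUDs, described as measures of fear level.
2. Add the within-session slope of the 5-minute SUDs ratings as the measure of improvement. Fit a mixed model to the individual ratings in sessions 2-6 with arm, time within session, session and their interactions, and participant-level random effects. Test arm-by-time, averaged over the five sessions. The six-session minimum in section 6.0 makes these sessions due for everyone; later ones depend on response.
3. Do not adjust the main comparison for each session's initial SUDs. Report initial SUDs by arm beside the slope, and present any adjusted model only as a labelled sensitivity analysis.
4. Prefer the slope to peak minus last. It uses all ratings and leans less on when exposure stopped, though it is still limited by a low start and must be read with initial SUDs.
5. Reconcile section 10.2 with the per-session list. Either delete heart rate and skin conductance from the within-session analysis and rely on the assessment-visit recordings, or, if session recording is intended, add it to Measures at each Therapy Session.

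Items 1 to 4 cost SAP wording and a little more analysis, with no new data. Deletion under item 5 costs nothing; session recording would need set-up time at each session.

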repeated measures ANCOVA will be used to obtain adjusted means, mean differences and interaction terms for continuous outcomes. For each of these analyses, the baseline measure for each specific outcome will be included as a covariate in the analysis.

*GEE Modeling for analysis of entire 12-month assessment period:* Additionally, to evaluate treatment effects for the entire 12-month follow up period, logistic and linear generalized estimating equation (GEE) regression models will be used for dichotomous and continuous variables respectively. GEE modeling is an appropriate analytic tool for longitudinal, repeated measures data as it is designed to adjust for within-subject correlations over time (Liang & Zeger, 1986; Kleinbaum et al., 1998; Hardin & Hilbe, 2003). By using the GEE method, the relationship between outcome variables obtained at different assessment time points and predictor variables are analyzed simultaneously. GEE models are comprised of a time independent variable (i.e. treatment condition) and a time-dependent variable (i.e. key outcomes variables and covariates). The estimated coefficients reflect the relationship between the time-independent and time-dependent using all available longitudinal data. Since repeated observations within one subject are not independent of each other, a correction must be implemented to account for within-subject correlations. This correction is achieved by assuming an a priori correlation structure for the repeated measurements of the outcome variables. It is proposed that the autoregressive correlation structure will be utilized. The assumption behind the autoregressive correlation structure is that the correlation between responses is dependent on the interval of time between responses. The resulting GEE parameters can be interpreted as the odds or the mean difference for logistic and linear regression models respectively, over the entire 12-month period for an average participant. GEE analyses will be performed using STATA, version 8.0 (Stata Press, College Station, Texas) using the xtgee command with corr(ar1).

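### The 12-month GEE for Hypothesis 2 specifies no robust variance, so its standard errors hold only if an assumed autoregressive correlation is right (should-fix, cheap)

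*Combined protocol and SAP*

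**What the plan says.** Section 10.2, under GEE Modeling for analysis of entire 12-month assessment period, explains that repeated observations on one subject are dependent and need a correction. It then says: "This correction is achieved by assuming an a priori correlation structure for the repeated measurements of the outcome variables". It chooses an autoregressive structure and gives this reason: "The assumption behind the autoregressive correlation structure is that the correlation between responses is dependent on the interval of time between responses". The models are to be run in Stata "using the xtgee command with corr(ar1" as the correlation option. The coefficient is described as one treatment effect averaged over the 12 months.

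The section names no variance estimator, no time variable and no rule for unequal gaps, and does not list which visits are outcomes. Hypothesis 2, in section 2, concerns "a follow-up assessment gathered 3, 6, and 12 months post-treatment as compared to baseline". Section 8.0 schedules the same battery at post-treatment and at 3, 6 and 12 months. Counted from post-treatment, the gaps are 3, 3 and 6 months.

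The GEE is an additional analysis. Hypothesis 2 is tested first by interval-specific logistic regression and repeated measures ANCOVA, which do not use the autoregressive structure. The stated error rate, in the Power and Sample Size text, is: "We set the Type I Error rate at 0.05 (two-tailed) for all computations".

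**The concern.** A GEE estimate of a mean difference does not need the working correlation to be right, but its model-based standard error does. Here the assumed correlation is described as the whole correction, so followed as written the plan stakes the standard error on AR(1).

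AR(1) makes correlation fall geometrically towards zero as visits move apart. If some patients stay worse than others throughout the year, correlation between distant visits stays high. Each patient's four scores then carry less independent information than the model believes, the confidence interval for the DEX effect is too narrow, and the test rejects too often.

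This is the only model that covers the whole follow-up period, so it bears on Aim 2. A second, smaller point is that the stated rationale is elapsed time, whereas the command as written does not say what time scale it uses for gaps of 3, 3 and 6 months.

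**Working it through.** **The plan's own figures.** No figure is given for the GEE. The only sample size is for Hypothesis 1: "For a two-group study design, 100 participants", 50 per arm, with a "minimum desired power of 85% to detect an effect size of" 0.65. It reproduces: 2 × (1.960 + 1.036)² / 0.65² = 42.5, so 43 per arm (44 with the t distribution), and 44 / 0.9 = 48.9, so 49 per arm. It has no bearing on this point except to supply the numbers available. The plan assumes that "10% of participants will be lost to the" study by the end of treatment, and 50 × 0.9 = 45 per arm. A further 10% of completers are expected to be lost before 3 months; no rate is given for 6 or 12 months, so 40 per arm is used as an assumption.

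**Assumptions.** Correlation of 0.3 to 0.8 between visits 3 months apart; continuous outcome; complete data; AR(1) applied by visit order.

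**Formulas.** With m visits and AR(1) parameter α (the mean correlation of adjacent visits), the end visits get weight proportional to 1 and the inner visits proportional to 1 − α. In units of the single-visit variance:

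- Model-based variance = (1 + α) / [2 + (m − 2)(1 − α)].
- True variance = w′Rw, with w the weights scaled to sum to 1 and R the true correlation matrix.
- k = √(model-based / true); type I error = 2[1 − Φ(1.96k)].

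**Constant correlation 0.5, four visits.**

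- α = 0.5; weights 1/3, 1/6, 1/6, 1/3.
- Model-based: 1.5 / 3 = 0.500.
- True: 0.5 + 0.5 × (2/9 + 2/36) = 0.639.
- k = √(0.500 / 0.639) = 0.885; 1.96k = 1.734; type I error 8.3%.
- Over correlations 0.3 to 0.8: k = 0.885 to 0.927, type I error 6.9-8.3%.

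**Constant correlation 0.5, visits at 3, 6 and 12 months only.**

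- Weights 0.4, 0.2, 0.4. Model-based: 1.5 / 2.5 = 0.600.
- True: 0.5 + 0.5 × 0.36 = 0.680.
- k = 0.939; type I error 6.6%. Over 0.3 to 0.8: 5.9-6.6%.

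**Correlation decaying exactly with months (0.5 per 3 months), four visits.** Only the spacing is misspecified here.

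- α = (0.5 + 0.5 + 0.25) / 3 = 0.417; weights 0.316, 0.184, 0.184, 0.316.
- Model-based 0.447, true 0.445; k = 1.003; type I error 4.9%. Over 0.3 to 0.8: 4.9-5.0%.

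**Part stable, part decaying.** Let correlation be f + (1 − f)q^(gap/3), with gap in months.

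- If 60% of the 3-month correlation is stable and that correlation is 0.5, then f = 0.3 and q = 0.2 / 0.7 = 0.286. The 6-month correlation is 0.3 + 0.7 × 0.286² = 0.357, so α = 0.452. Model-based 0.469, true 0.541, k = 0.931, type I error 6.8%.
- The same split at 3-month correlations of 0.3, 0.5, 0.7 and 0.8 gives 5.7-6.8%.
- With f = 0.3 to 0.5 and q = 0.5 to 0.8, four visits give 5.2-6.2% and three visits 5.1-5.5%.

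**Simulation.** 10,000 null trials per case, four visits, 40 and 50 per arm, α estimated, normal reference:

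| True correlation | Model-based | Robust |
|---|---|---|
| Visit-order or elapsed-time AR(1) | 5.0-5.6% | 5.3-5.9% |
| Constant, 0.5 to 0.8 | 7.6-8.9% | 5.3-6.0% |

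A separate run at 45 per arm under constant correlation gave 8.3-8.9% model-based against 5.0-5.7% robust.

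**Cost of keeping AR(1) weights.** With constant correlation 0.5 the best variance is (1 + 3 × 0.5) / 4 = 0.625, against 0.639 with AR(1) weights, an efficiency of 0.978. The lowest four-visit efficiency in the cases tried was 0.973.

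**The case against.** The strongest reply is that the harm is conditional and confined to one supplementary model. Robust variance is not mentioned, but neither is it ruled out. The GEE comes after the interval-specific analyses, in a trial titled a pilot whose aims are exploratory and whose sample size was set on Hypothesis 1. The upper end of the error range needs perfectly constant correlation and post-treatment counted as a GEE outcome, and the documents establish neither. All of this stands, and it limits the severity. It does not remove the point: a plan that fixes the command and the correlation option, and says the correction comes from the assumed structure, should also fix the variance estimator before the data are seen.

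A reader might infer three stronger things that the documents do not support.

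- That unequal spacing makes the P values wrong. With spacing as the only error, the averaged test stays at about 5%; the inflation comes from correlation that persists.
- That the model lags by visit order. The text describes elapsed time and names no time variable, and how the software treats the 6-month gap cannot be settled from the documents. What can be said is that description and command need reconciling.
- That individual visit comparisons are distorted. If treatment-by-visit contrasts were fitted in this GEE and correlation decayed with months (0.6 to 0.8 per 3 months), simulation at 45 per arm gives 9.0-10.0% rejection for the 6-to-12-month contrast and 2.7-3.2% for the post-to-3-month contrast. The GEE text plans one averaged effect and no such contrasts.

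**Conclusion.** The point holds as a should-fix. As written, the validity of the 12-month GEE standard errors and P values rests on an autoregressive structure for which the plan offers no evidence. For the averaged effect at a nominal two-sided 5%, the type I error is about 5% under decay with time, about 5-7% for part-stable correlation, and about 7-9% under constant correlation with four visits (5.9-6.6% with 3, 6 and 12 months only). Robust variance returns it to about 5-6%.

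These sizes rest on assumed correlations, a continuous outcome, complete data and a visit-order AR(1). The logistic GEE and missing data were not simulated. It would go too far to say that the Hypothesis 2 P values are wrong: they can be too small, in this model only, if model-based variance is used and correlation persists.

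**What to change.** In section 10.2, specify participant-clustered robust standard errors for both the linear and the logistic GEE, with a t reference or a small-sample correction. The simulated robust error rates, slightly above 5% with a normal reference, show why the correction is wanted. AR(1) may stay as the working correlation, since the efficiency loss was under 3% in the cases tried. An unstructured correlation, or a mixed model for repeated measures for continuous outcomes, is optional and not needed for validity.

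In the same paragraph, name the outcome visits and the time variable and say how the 6-month gap is handled, or drop the statement that correlation depends on elapsed time.

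The cost is a few lines of text and one or two options in the code, with no new data or patients. The downside is slightly less stable standard errors with about 70-90 patients.
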